Pilot study on the association between allergic rhinitis and cognitive ability in children aged 11-14 within the same year group at school. Primary outcome measures include cognitive tests (Digit Span Test, Stroop Test, Chinese Auditory Verbal Learning Test, Verbal Fluency Test, and Trail Making Test), so as to assess the cognitive ability of allergic rhinitis patients before and after treatment compared to a control group. Rhinitis Symptom Utility Index (RSUI) of patients will be the secondary outcome measured through questionnaires. Positive skin prick test and endoscopy examination (taking place in Prince of Wales hospital) will be required before the diagnosis of allergic rhinitis. The data will be analyzed by the Multilevel models. Collectively, an estimate of 34 allergic rhinitis patients with 106 control samples are to be recruited in a secondary school. Written consent will be required prior to the study, and all participants have the right to withdraw from the study at anytime. Should any issues arise, subjects and their legal guardians may contact research staff [name] during office hours.

RESEARCH OBJECTIVES

1. To investigate, if any, the differences between normal and allergic rhinitis patients in terms of cognitive function
2. To investigate the impact of allergic rhinitis on different areas of cognitive function
3. To investigate the improvement of cognitive function in children after 8 weeks of standard treatment of allergic rhinitis

RESEARCH HYPOTHESIS

Children with allergic rhinitis are expected to have a heightened improvement in cognitive abilities after the treatment compared to the normal control group due to relief of their nasal symptoms.

STUDY DESIGN

This study is a prospective longitudinal pilot study to take place from 1 Dec 2017 to 31 Dec 2018. Final report will be completed 30 June 2019.

STUDY SAMPLE AND SETTING

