Students aged 11 to 14 currently studying Form 1 and 2 in secondary school will be recruited directly through invitation. Recruitment will include patients suffering from untreated allergic rhinitis in addition to healthy individuals to serve as a control group. Patients suffering from allergic rhinitis will be classified according to ARIA guidelines into mild/moderate/severe, and duration into intermittent/persistent. Patients suffering from rhinitis due to non-allergic origins or those associated with nasal polyposis or sinusitis will be excluded. Patients are going to complete the Rhinitis Symptom Utility Index (RSUI) questionnaire for assessing pre and post symptoms.

Control Group- Inclusion Criteria

1. Both genders of 11-14 years
2. Chinese in ethnicity
3. Subjects who have not been diagnosed with a long term medical or psychiatric problem
4. Subjects who are not currently undergoing any long term medical treatment.

Patient Group- Inclusion Criteria

1. Both genders of 11-14 years, diagnosed with allergic rhinitis on basis of screening instruments, medical history, clinical assessment (by general ORL examination including nasal endoscopy)
2. Chinese in ethnicity
3. Positive skin prick test with wheal diameter $\geq 3\text{mm}$

4. Ability to understand the nature, scope, and possible consequences of the study
5. Capability and willingness to comply with the requirements of the protocol

Patient Group- Exclusion Criteria

1. Subjects with co-existing nasal conditions other than AR, which may affect nasal pathology (nasal polyposis, sinusitis, severe deviations of nasal septum, tumors of the nasal cavity, acute/chronic rhinosinusitis or any underlying pathology that might affect nasal breathing or nocturnal sleep)
2. Subjects with prior nasal surgery (e.g. nasal cavity, sinuses)
3. Subjects with known brain disorders, prior brain surgery or history of stroke
4. Subjects diagnosed with learning disability, autism or attention deficit hyperactivity disorder (ADHD)
5. Subjects with history of known sleep disorder, central or obstructive sleep apnea, narcolepsy, insomnia, patients requiring regular sleep medication and those hypersensitive to applied topical nasal steroids
6. Subjects who have taken topical nasal steroids, oral anti-histamines or medications affecting nasal symptoms 30 days prior to commencement of study
7. Subjects with hypersensitivity reactions towards topical nasal steroids or oral anti-histamines

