8. Subjects previously diagnosed with any psychiatric disorders
9. Subjects who suffered from a respiratory tract infection within the past 30 days
10. Subjects who have clinically major cardiovascular, respiratory, hepatic, neurological, endocrine, immunological or other major systemic disease(s)
11. Subjects who are undergoing a long-term medical treatment plan

TREATMENT AND COMPLIANCE

Medication (complying with standard treatment guidelines) will be prescribed to the patient group. As this study does not investigate the efficacy of a specific drug, the medication plan will be up to the discretion of the attending physician with the aim of alleviating nasal symptoms. Commonly, pediatric allergic rhinitis treatment involves topical nasal steroids and 2nd generation antihistamines. Compliance will be monitored via the treatment diary, phone call after four weeks of treatment, and pill counting. Should issues arise anytime during the study, research staff will be available for subjects to contact during office hours. To increase the incentives of the participants, reinforcement programs, such as hospital visits and a health-related seminar, will be held. Each participant will receive a certificate upon completion.

METHOD OF ANALYSIS

Multilevel models, the mixed effects models [19], will be used to compare the longitudinal rate of change on cognitive function and different areas of cognitive function (as measured by Digit Span Test, Stroop Test, Chinese Auditory Verbal Learning Test, Verbal Fluency Test, and Trail Making Test) both within and between normal and allergic rhinitis patients. Multilevel models are random effects models that take into account the hierarchical nature of the data, and the within- and between-subject heterogeneity [20]. For longitudinal data, such models allow for measurements made at unequal intervals and with a varied number of measurements (i.e. subjects who may have one or several measurements). The models are fitted by the method of restricted iterative generalized least-squares algorithm of MLn for Windows software package, Version 2.0 (Institute of Education, University of London, London, UK). The likelihood ratio test is used to assess the statistical significance of the estimates at the 5% level. The model assumptions are checked by inspection of the standardized residuals for normality and constant variance.

PROPOSED TIMELINE

Week 0

- A. Consent will be sought from potential subjects

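### Controls must be free of any diagnosed long-term medical problem, but patients are barred for general medical disease only when it is clinically major, so the baseline contrast can include the effect of other conditions

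*Combined protocol and SAP*

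**What the plan says.** The eligibility lists are in Subjects and Method of the combined protocol and SAP.

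- **Controls, inclusion item 3:** "Subjects who have not been diagnosed with a long term medical or psychiatric problem". No severity threshold is attached.
- **Controls, inclusion item 4:** "Subjects who are not currently undergoing any long term medical treatment".
- **Patients, exclusion item 10:** "Subjects who have clinically major cardiovascular, respiratory, hepatic, neurological, endocrine, immunological or other major systemic disease(s". Only major disease is barred.
- **Patients, exclusion item 11:** "Subjects who are undergoing a long-term medical treatment plan". This matches control item 4.
- **Patients, exclusion item 8:** "Subjects previously diagnosed with any psychiatric disorders". This broadly matches the psychiatric half of control item 3.
- **Patients, other exclusions:** items 1 to 5 and 9 bar other nasal or breathing pathology, previous nasal surgery, brain disorders, learning disability, autism and ADHD, sleep disorders, and respiratory infection in the preceding 30 days. Items 6 and 7 concern recent rhinitis medication and drug hypersensitivity. The control section has no exclusion list.

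Objective 1 compares normal children with rhinitis patients. Objective 2 is "To investigate the impact of allergic rhinitis on different areas of cognitive function". Method of Analysis specifies mixed models for change within and between the groups. It names no covariates, and nothing in the document matches the groups on other conditions.

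**The concern.** Attributing a cognitive difference to rhinitis, as Objective 2 does, needs groups that are alike in other respects that bear on the tests. Here one group is cleared of every diagnosed long-term medical problem and the other only of major ones. A child with a mild diagnosed condition such as asthma or eczema, not on long-term treatment and not caught by patient items 1 to 9, is eligible on the patient side and ineligible on the control side. If such conditions lower test scores at all, the lower scores fall in the patient group and would be read as an effect of rhinitis. Copying the patient exclusions onto the control list would not remove this mismatch, because it arises where the control rule is the stricter one.

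**Working it through.** **Plan's own figures.** From Study Sample and Setting: 200 students x 0.70 participation = 140; 140 x 0.245 prevalence = 34.3, stated as 34; 140 - 34 = 106 controls, as stated in the Brief Summary. These reproduce. They are feasibility counts; the document gives no effect size, SD or power calculation.

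**Where the lists differ.**

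| Domain | Controls | Patients | Parallel? |
|---|---|---|---|
| Long-term treatment | barred (item 4) | barred (item 11) | yes |
| Psychiatric diagnosis | barred if long-term (item 3) | any previous diagnosis barred (item 8) | broadly |
| General medical condition | any diagnosed long-term problem barred (item 3) | only clinically major barred (item 10) | no, controls stricter |
| Learning disability | not named | barred (item 4) | no, patients stricter |
| Recent respiratory infection | not named | barred (item 9) | no, patients stricter |
| Brain and sleep disorders | not named; a diagnosed long-term one falls under item 3 | barred (items 3 and 5) | partly |

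The gap at issue is the third row: conditions that are diagnosed, non-major, untreated and not named in patient items 1 to 9.

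**Size of that component.** The share of patients with such a condition and its effect on scores are assumptions; the document gives neither.

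- Bias b (in SD) = share of patients affected x effect in SD.
- SE of the baseline difference = sqrt(1/34 + 1/106) = 0.197 SD.
- With no true rhinitis effect, the two-sided 5% rejection rate is P(Z > 1.96 - b/SE) + P(Z < -1.96 - b/SE). The plan states the 5% level but not the sidedness; two-sided is assumed.

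| Share x effect | b (SD) | b/SE | Rejection rate |
|---|---|---|---|
| 20% x 0.2 SD | 0.04 | 0.20 | 5.5% |
| 40% x 0.3 SD | 0.12 | 0.61 | 9.3% |
| 40% x 0.4 SD | 0.16 | 0.81 | 12.8% |
| 50% x 0.4 SD | 0.20 | 1.01 | 17.4% |

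The rate passes 10% at a bias of about 0.13 SD.

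**The opposing component.** Suppose, again as an assumption, that 2% to 10% of controls have a condition barred only among patients and that it costs 0.5 to 1.0 SD. Control scores are then lowered by 0.02 x 0.5 = 0.01 SD to 0.10 x 1.0 = 0.10 SD.

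**Net.** Counting a push toward a rhinitis deficit as positive, the total lies between 0.04 - 0.10 = -0.06 SD and 0.20 - 0.01 = +0.19 SD. The range includes zero, so the sign cannot be fixed.

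**Change contrast.** A condition that shifts a child's score equally at Week 2 and Week 10 drops out of that child's change. Objective 3 is therefore little affected, provided the effect of the condition is stable over the 8 weeks.

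**The case against.** The strongest reply is that the gap is narrow. Patients are already screened for brain, sleep, neurodevelopmental and psychiatric conditions, which are among those most likely to affect cognitive tests, and long-term treatment is barred in both groups. What remains is by definition non-major and untreated. Rejection rates above 9% need at least 40% of patients to carry a condition costing 0.3 SD or more; at 20% x 0.2 SD the rate is essentially nominal. The research hypothesis concerns improvement after treatment, where a stable condition largely cancels. Objective 1 asks only how patients differ from normal children, and this is a pilot.

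Most of this stands, and it limits the point to the baseline contrast and to a modest size. It does not remove it: Objective 2 uses causal language, and nothing in the analysis plan separates rhinitis from accompanying conditions.

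A reader might also infer two stronger things. One is that patients are barred only for major disease or long-term treatment; the other patient exclusions contradict that. The other is that the comparison as a whole is tilted toward a rhinitis deficit. The documents do not support that either: learning disability need not count as a long-term medical or psychiatric problem, a recent respiratory infection does not, and both are barred among patients only.

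**Conclusion.** The mismatch is real and can be read directly from the two lists. It allows other conditions to contribute to the baseline patient-control difference used for Objectives 1 and 2. As a single component it favours a deficit in patients, by 0.04 to 0.20 SD under the assumed shares and effects, which is 0.2 to 1.0 standard errors at 34 and 106 children. The rejection rates of 5.5% to 17.4% describe that component in isolation. They are not an estimate of the study's actual error rate, because an opposing component of unknown size is also present. Confidence in the magnitude is low. The point justifies a cheap safeguard; it does not invalidate the design.

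**What to change.** 1. Leave control item 3 in place. Loosening it alone would admit controls with, for example, a non-major sleep or brain disorder that patients must not have.
2. At the Week 1 medical history, which the Proposed Timeline already includes for children with suspected rhinitis, record every other diagnosed long-term condition.
3. Prespecify a sensitivity analysis that repeats the Objective 1 and 2 contrasts in patients who meet control item 3 apart from rhinitis. Report the full and restricted estimates, each with a confidence interval, and attribute a difference to rhinitis only with the restricted estimate shown alongside.
4. If the criteria can still be changed, apply one common health standard to both groups, including the cognitive, sleep and brain exclusions now listed for patients only.

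**Cost.** Steps 1 to 3 need no new visit and no change to controls. The price is precision in the restricted analysis. If 24 of the 34 patients qualified (an illustration), the SE would be sqrt(1/24 + 1/106) = 0.226 SD, and the 95% half-width would rise from 1.96 x 0.197 = 0.39 SD to 1.96 x 0.226 = 0.44 SD. Disagreement between the two estimates should therefore be judged from the intervals, not from whether each crosses the 5% level. Step 4 needs an amendment to the criteria and would remove some otherwise eligible children.

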To test selective attention, response inhibition and speed of information processing, the Victoria Stroop Test will be utilized. With the administration time of approximately 5 minutes, the Victoria Stroop Test is a shortened, psychometrically sound version of the original Stroop Colour-Word Test. Participants will be shown 3 cards in total, with his/her response time to each card being recorded. The first card will show dots of differing colours, with participants being asked to recite the colours shown. The second card contains a list of random words printed in different colours and the participant will be asked to name the colour of the words. The third and last card contains colour words printed in ink that is coloured different from the word, with the participant being asked to name the colour rather than read the word. The difference in the time required to respond to each of these colours allows the measurement of interference and hence the Stroop effect. The Stroop Colour and Word Test has previously been used to assess cognitive function in allergic rhinitis patients^[11] and also depressive patients^[12].

Chinese Auditory Verbal Learning Test

For assessment of verbal learning and memory domain, the Chinese Auditory Verbal Learning Test will be utilized. This test, based on the original Rey Auditory Verbal Learning Test, was developed by local researchers and psychologists, and has been used previously on Chinese adolescents^[9]. Participants are presented with a list of 15 words (List A), and are asked to read this list aloud 5 times, with each time being followed by a free recall. Following this, an interference list of 15 words (List B) will be presented to the participant. Participants will be asked to read aloud and recall the interference list (List B), and then to recall the words from List A without further presentation. After a 30 minute delay, the participants will once again be asked to recall the words from List A without regard to order. The number of words recalled will be used as a measurement of memory retrieval. Afterwards, a list of words will be presented to the participants and they will have to recognize those that originated from List A.

Verbal Fluency Test

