Participants will be given a category and asked to list as many words as possible relating to the category (e.g. vegetables). The number of words spontaneously produced within 1 minute will be measured and used to assess one of the executive functions, semantic fluency. The Word Fluency Test has previously been used in multiple neuropsychological studies^[13] and also as a tool for measuring executive functions in children ^[14].

Trail Making Test

Participants will be given two sheets and asked to draw a line to connect the circled numbers from smallest to largest numerically in Part A, and draw a line to connect first a circled number and then a circled alphabet in numerical and alphabetical way alternatively. The test will take 5 to 10 minutes and be used to assess one of the executive functions, selective attention. The Trail Making Test has previously been used in psychometric studies[21] and also as a tool for measuring executive functions in children.

Skin Prick Test

Widely-used test used to identify allergens responsible for triggering symptoms of type I hypersensitivity reactions. It is regarded as a safe method of investigating sensitization in children[15]. Different types of allergen will be exposed to the body through the skin. A wheal diameter $\geq 3\text{mm}$ will be considered positive.

Screening Questionnaire

To screen out healthy individuals and individuals with allergic rhinitis, a screening questionnaire adopted from ISAAC (International Study of Asthma and Allergies in Childhood) Core Manual and supplementary questionnaires on rhinitis and rhinitis management[16] with extra questions added according to ARIA (Allergic Rhinitis and its Impact on Asthma) classification. ISAAC and ARIA have been shown to be useful in evaluating prevalence and severity of allergic rhinitis in school children[17]. Baseline Total Nasal Symptom Score (TNSS)[18] will also be evaluated in the questionnaire (Appendix 3).

Treatment Diary

Subjects are required to fill in an 8-week diary for drug compliance monitoring (Appendix 5). Everyday subjects are required to fill in the time at which they took the medication and are given the opportunity to jot down additional remarks. This is to ensure treatment compliance, and not for the interpretation of treatment outcomes.

SUBJECTS AND METHOD

Subjects

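### The plan fits every model by restricted likelihood and tests by likelihood ratio without saying which likelihood; a restricted ratio would not hold 5% for the fixed effects of interest

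*Combined protocol and SAP*

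**What the plan says.** The combined protocol and SAP sets out the analysis in one paragraph, METHOD OF ANALYSIS. Mixed models will "compare the longitudinal rate of change on cognitive function and different areas of cognitive function", both within and between the two groups. Estimation and testing are covered by two adjacent sentences:

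- Estimation: "The models are fitted by the method of restricted iterative generalized least-squares algorithm of MLn for Windows software package", Version 2.0.
- Testing: "The likelihood ratio test is used to assess the statistical significance of the estimates at the 5% level".

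No other fit is named, no Wald, t or F test is named, and nothing limits the tested estimates to variance terms.

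RESEARCH HYPOTHESIS states what the analysis must show: "Children with allergic rhinitis are expected to have a heightened improvement in cognitive abilities after the treatment compared to the normal control group". In model terms this is a group × time effect; the term is mine, as the plan does not write the model out.

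Outcome scales differ. For the Stroop Test each participant is shown three cards, "with his/her response time to each card being recorded"; for the Verbal Fluency Test, "The number of words spontaneously produced within 1 minute will be measured". The unit of the timed scores is not given. PROPOSED TIMELINE places cognitive testing at Week 2 and Week 10, but how time is coded in the model is not stated.

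**The concern.** A restricted likelihood is the likelihood of what remains of the data after the fixed part of the model has been removed. Two models with the same fixed part can be compared on it. Two models with different fixed parts cannot, because each likelihood then refers to a different reduced data set. Twice the log ratio does not follow a chi-square distribution, and it changes when the outcome is rescaled.

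This matters because the tests the study needs are of that second kind. The group × time effect carries the hypothesis and objective 3, and the patient–control difference in objective 1 is also a fixed effect. If the two sentences are followed by comparing restricted likelihoods, the same data could pass or fail at 5% according to the unit in which a response time is entered, and the five cognitive tests would be judged at different, unknown error rates.

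**Working it through.** **Inputs from the document.** Form size about 200, participation 70% and prevalence 24.5% (STUDY SAMPLE AND SETTING). 200 × 0.70 = 140; 140 × 0.245 = 34.3, taken as 34; 140 − 34 = 106. The planned 34 and 106 reproduce. Two cognitive assessments 8 weeks apart. Nominal level 5%, so the 1 df critical value is 3.84.

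**Assumptions not in the document.** Outcome SD 1, 4 or 20 units; within-child correlation 0.7 (0.5 to 0.9 as a range); random intercept; complete data; true group × time effect zero.

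**Step 1: effect of units (no assumption about SD, correlation or sample size).** Multiplying the outcome by c raises −2 log restricted likelihood by (N − p) ln c², where N is the number of observations and p the number of fixed effects. The models with and without one fixed effect differ by 1 in p, so the test statistic rises by 2 ln c.

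- Seconds to tenths of a second: 2 ln 10 = +4.61, more than the critical value itself.
- Time coded 0/8 (weeks) instead of 0/1: −2 ln 8 = −4.16 in the usual form. This shift vanishes if the restricted likelihood is normalised by |X′X|; the outcome-unit shift does not.
- Full likelihood: both shifts are 0.

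One simulated data set shows this. The full-likelihood statistic was 0.794 in every coding. The restricted statistic was 3.94 (seconds, time 0/1), −0.22 (seconds, weeks), −4.25 (minutes, 0/1) and 17.76 (milliseconds, 0/1).

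**Step 2: true level.** To a close approximation the restricted statistic equals the Wald statistic plus ln(2π·V), with V = s²(1/34 + 1/106)/T². Here s² = 2·SD²·(1 − correlation) is the variance of change and T the coded time span. Software that omits the 2π constant adds ln V instead. The bracket is 0.02941 + 0.00943 = 0.03885.

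Example: SD 4, correlation 0.7, T = 1. Then s² = 2 × 16 × 0.3 = 9.6, V = 0.373 and ln(2π × 0.373) = 0.85. The test rejects when the Wald statistic exceeds 3.84 − 0.85 = 2.99, which has probability about 8.4% under the null.

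Exact closed form, by simulation, at correlation 0.7:

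| Likelihood compared | Time coding | SD 1 | SD 4 | SD 20 |
|---|---|---|---|---|
| Restricted, 2π kept | 0/1 | 1.7% | 8.4% | 99% |
| Restricted, 2π dropped | 0/1 | 0.6% | 2.8% | 21% |
| Restricted, 2π kept | weeks | 0.2% | 0.8% | 4.8% |
| Full (ML refit) | any | 5.2% | 5.2% | 5.2% |

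Over correlations 0.5 to 0.9 with 2π kept, the restricted levels are 0.9–2.2%, 4.3–12% and 35–100% with time 0/1. In weeks they run from 0.09% to 6.5% over all nine combinations, eight of them below 5%.

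**Step 3: procedures that hold the level.** Full maximum likelihood refit, about 5.2%; full likelihood evaluated at the RIGLS estimates, about 5.1%; Wald chi-square from the RIGLS fit, about 5.2%; t test on 138 df, about 5.0%. Direct mixed-model fits (300 data sets per cell, SD 1 / 4 / 20, time 0/1, 2π kept), with about 15% of Week 10 visits missing, gave the same picture: restricted 1.0 / 8.0 / 100%, full 6.3 / 5.3 / 4.0%.

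**The case against.** The strongest reply is that the plan never says the ratio is of restricted likelihoods. One sentence names an estimation algorithm and the next an unqualified test. Taking the ordinary likelihood at the RIGLS estimates fits the words equally well, and then the level is about 5%. This stands. A reader might infer that the plan commits to an invalid test, or that the final analysis will be wrong. The document supports neither: it does not say which likelihood the software reports or which one the analyst will use.

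A reader might also infer a large excess of false positives from the 99% figure. That figure needs an SD of 20 units, time coded 0/1 and the 2π constant kept, none of which the document gives. Dropping the constant brings it to 21%. The plan's language of rates of change and unequal intervals suggests elapsed time, and with time in weeks the level is mostly below 5%, so the likelier harm would be lost power. The direction of error is therefore not fixed.

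Two further replies carry less weight. The study is a pilot, but it still commits to tests at 5%. A statistician may well know to refit, but the text names only the restricted fit, and the refit is not in the plan.

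**Conclusion.** The point holds as a conditional one. The plan pairs a restricted-likelihood fit with a likelihood ratio test of fixed effects and leaves open which likelihood is compared. If it is the restricted one, the test of the main hypothesis is not chi-square and depends on units, and its true level could lie far below or far above 5%. The 4.61 shift for a tenfold change of outcome unit is exact; the levels themselves are illustrations resting on assumed SDs, correlation, time coding and software convention. If it is the full likelihood, the level is about 5.2% and nothing is wrong beyond the omission. Restricted-likelihood comparison of variance structures with the same fixed effects is not in question. Because one available reading gives a wrong test and the remedy is nearly free, this should be settled before analysis.

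**What to change.** Amend both sentences, not only the second. Rewording the test sentence alone would leave the preceding one naming RIGLS as the sole fit, and the 5% level must be carried over. Suggested text:

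*Fixed effects (group, time, group × time) will be tested at the 5% level by likelihood ratio on models fitted by IGLS (full maximum likelihood); final estimates and standard errors will be reported from RIGLS, and restricted likelihoods will be compared only between models with the same fixed effects.*

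An acceptable alternative is to keep RIGLS throughout and test fixed effects at the 5% level by Wald or t test from that fit. If the value reported by the software is already the full likelihood, a statement to that effect settles the matter.

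The cost is two reworded sentences and one extra fit per test, with no change to data collection or participants.
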